### **3.5 Study Completion and Withdrawal Criteria**

It is the right and duty of the Investigator to discontinue the study participation of a subject when the subject's health or well-being is threatened by continuation in the study. Such subjects should be withdrawn from the study and not continued under a modified regimen.

The following are circumstances that would result in the subject's discontinuation from the study:

- The subject experiences a serious adverse event rendering them unable to continue study participation;
- The subject is unable to physically or mentally tolerate the use of the least medication;
- An exclusion criterion becomes apparent at any time during the study, or the subject voluntarily withdraws.

In the event of premature discontinuation from the study, the Investigator should determine the primary reason for discontinuation. A subject who is withdrawn from the study prior to initiation of treatment may be replaced.

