## **1. STATEMENT OF HYPOTHESIS AND OBJECTIVES:**

Surgical procedures are an essential piece of a dermatologist's practice. In fact, it has been reported that dermatologists perform over 25 million minor surgical procedures annually. A major focus of these procedures is to restore the integrity of the skin while minimizing scarring and potential complications. With dermatologic surgeries being so numerous, there is much discussion about how to optimize post-surgical wound care while decreasing potential barriers to healing. Recent advances in wound therapy have resulted in the development of advanced wound care therapies, such as collagen-based dressings, for use as adjunctive therapies to combat the molecular defects present in wounds.

We have designed a pilot study investigating the efficacy of Nuvagen™ (collagen powder) in treating skin punch biopsy wounds. The objectives of the study are as follows:

Primary objective:

1. To evaluate the effect of Nuvagen™ (collagen powder) on complete wound healing using punch biopsy sites as an acute full-thickness human wound model based on clinical wound closure.
2. To evaluate the effect of Nuvagen™ (collagen powder) on complete wound healing using punch biopsy sites as an acute full-thickness human wound model based on histology of wound site at 4 weeks following injury.

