#### **Exclusion:**

- Patients less than 18 years and greater than 75 years of age
- Patients that have any medical or skin condition that could impair wound healing
- Patients that have used systemic medications that suppress the immune system within 5 half-lives (if known), or 2 months of enrollment (i.e. corticosteroids)
- Patients that have applied topical steroids to the thigh(s) in the 2 weeks prior to enrollment
- Patients that are currently participating in an investigational study of a drug or device or have participated within 4 weeks of enrollment
- Patients that in the opinion of the investigator demonstrate evidence of unwillingness or inability to follow instructions or to complete the study
- Patients currently using systemic antimicrobials
- Patients with a history of diabetes mellitus
- Patients with a history of bleeding disorders or concomitant treatment with aspirin or anticoagulants (including heparin, low molecular weight heparin, warfarin, fondaparinux, or rivaroxaban)
- Patients with a history of keloids or hypertrophic scars
- Patients with other conditions considered by the investigator to be reasons for disqualification that may jeopardize subject safety or interfere with the objectives of the trial (e.g., acute illness or exacerbation of chronic illness)
- Patients with a known allergy or sensitivity to any component of the test medication (including bovine and/or collagen products) or local anesthetic agent used
- Current or previous users of tobacco products
- Recent alcohol or drug abuse is evident

- Pregnant females or nursing mothers. Eligible women of reproductive age will be required to have a negative urine pregnancy test at screening. They will also be required to be on at least 1 reliable form of effective birth control [examples: *barrier method (condoms, diaphragm), oral, injectable, implant birth control or abstinence*] during the course of this study and 30 days following the last treatment period.

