### 3.3 Screening Phase

Prior to wounding and treatment, potential participants will be evaluated for study eligibility. All inclusion and exclusion criteria must be met prior to study entry and enrollment.

The patient's first visit will comprise both screening and wounding. During the screening phase, after obtaining signed informed consent, subject's personal data will be recorded. Data will include age, gender, medical and medication history and skin type. The physical examination will be performed and vital signs will be obtained. If the subject qualifies, visit 1 procedures will follow in the same visit.

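### Section 3.5 ends study participation, not only treatment, when a subject cannot tolerate the medication, and the plan provides no wound assessment afterwards

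*Combined protocol and SAP*

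**What the plan says.** Section 3.5 lists circumstances that lead to discontinuation from the study. It has no separate category for stopping treatment only. Three bullets matter here:

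- Intolerance: "The subject is unable to physically or mentally tolerate the use of the least medication".
- Exclusion criteria and voluntary withdrawal: "An exclusion criterion becomes apparent at any time during the study, or the subject voluntarily withdraws".
- Serious adverse events: "The subject experiences a serious adverse event rendering them unable to continue study participation".

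For subjects whose health is threatened, the paragraph before the list also rules out carrying on under an altered regimen. The one step required after discontinuation is stated as follows: "the Investigator should determine the primary reason for discontinuation". Replacement is allowed only before treatment starts.

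The exclusion list in section 3.2 includes "Patients currently using systemic antimicrobials", with no exemption for treating a study-wound infection. Section 3.3 ties the criteria to entry: "All inclusion and exclusion criteria must be met prior to study entry and enrollment". The second primary objective in section 1 assesses healing "based on histology of wound site at 4 weeks following injury". The tissue for this comes from the re-biopsy at visit 4.

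**The concern.** The trial compares two wounds within each of 8 subjects. A rule that takes the whole subject out because of one wound also ends measurement of the other. If the trigger is linked to how a wound is doing, then whether later measurements exist depends partly on the outcome being studied.

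Section 4.3 plans description only and has no rule for missing data or withdrawals. The closure counts and histology summaries are therefore the result itself. If complications are similar under the two treatments, the loss favours neither. If one treatment causes more of them, its later poor results are the ones that go unmeasured. No hypothesis test is at stake.

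**Working it through.** The plan states no withdrawal rate, so there is no figure to reproduce. The check compares the texts and then counts what one withdrawal costs.

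**Intolerance bullet.** The word *least* is apparently a slip for *test*. Section 3.2 uses that term for the collagen product when it excludes allergy to "any component of the test medication (including bovine and/or collagen products"). On that reading the trigger comes from the collagen wound alone, while its consequence falls on both wounds.

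**Exclusion-criterion bullet.** Two readings are possible.

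- *Present at entry, found late.* This fits the idea of a criterion coming to light, and it fits section 3.3. The serious-adverse-event bullet points the same way, since it removes only subjects who cannot go on.
- *Arising on study.* The bullet sets no limit to conditions present at entry. Section 5.1 requires a negative pregnancy test before each treatment session, so at least one criterion is meant to be watched during the study. On this reading, systemic antimicrobials for an infected study wound would qualify.

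**Follow-up after discontinuation.** Sections 3.4, 3.5, 4.3 and 5.4 and Table 1 contain no early-termination visit and no continued wound assessment for a subject who has left.

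**What one withdrawal costs.** Inputs are 8 subjects (section 3.2), one wound per thigh (section 3.4), and assessments at weeks 1, 2, 4, 6 and 12 with re-biopsy at week 4 (Table 1). The number lost, k, is an assumption.

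- Share of pairs per subject lost: 1/8 = 12.5%.
- Histology pairs left if k subjects leave before visit 4: 8 − 1 = 7, or 8 − 2 = 6.
- Original wounds have 3 looks (weeks 1, 2 and 4). Leaving at visit 2 loses 2 of 3; leaving at visit 3 loses 1 of 3.
- Second wounds have 2 looks (weeks 6 and 12). Leaving between visits 4 and 5 loses 2 of 2; leaving at visit 5 loses 1 of 2.

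**Effect on a reported closure count at week 4.** This assumes that subjects who left are dropped from the denominator (section 4.3 does not say) and that every remaining wound is closed.

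| k lost | Could be reported | Full count | Largest gap |
|---|---|---|---|
| 1 | 7/7 = 100% | 7/8 = 87.5% to 8/8 = 100% | 12.5 points |
| 2 | 6/6 = 100% | 6/8 = 75% to 8/8 = 100% | 25 points |

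**The case against.** The strongest reply concerns the exclusion-criterion bullet. The ordinary sense of its wording is that something already there has been discovered. A strict on-study reading also proves too much: section 3.2 excludes people currently taking part in an investigational study, so carried forward literally it would remove everyone on enrolment. Infection is an anticipated risk in section 5.2, and section 5.4 monitors such risks without mentioning withdrawal. This largely stands. A reader might infer that the protocol requires a subject treated for an infected study wound to leave; the documents do not support that. What remains is an ambiguity that staff could resolve differently for similar subjects.

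On intolerance, the reply is that *least* is read as *test* by inference. Stopping collagen while staying in the study is also already an ordinary path, because at visits 3 and 5 the investigator decides whether more is needed. That decision concerns need, not intolerance, and the intolerance bullet leads to leaving the study, so the reply answers the point only in part.

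It is also fair to say that the protocol is silent on later follow-up and does not forbid it. Subjects are told to report symptoms (section 5.4) and the reason for leaving is established, so the event itself would be known. Closure data already collected at weeks 1 and 2 remain, and the first primary objective fixes no time point. Finally, any dropout among 8 subjects would shift the counts in this way, and taking volunteers out entirely is a defensible protection. These replies limit the weight of the point. They do not explain why the sutured wound should go unmeasured when only the powder is not tolerated.

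**Conclusion.** The point stands as a low-cost improvement, not a serious flaw. For intolerance, section 3.5 links stopping treatment to leaving the study, and nothing provides for measuring either wound afterwards. This rests on reading the medication as the collagen product. The exclusion-criterion bullet is a secondary matter of unclear wording.

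The cost is 1 of 8 pairs per subject lost, including week-4 histology if the loss comes before visit 4. The number of such losses is unknown. A reader might be tempted to apply the infection rate of about 1 in 6 quoted in section 5.2: over the first two biopsies, 1 − (5/6)² = 30.6% of subjects, or 8 × 0.306 = 2.4 of 8. That is not an expected number of withdrawals. It needs independent wounds, systemic treatment of every infection and the on-study reading of the bullet. Section 5.2 itself says the source included patients with conditions that favour infection, whom this trial excludes. No intolerance rate is given either.

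A reader might also infer that the rule favours collagen. The documents do not establish a direction: that depends on complication rates by treatment, which they do not give.

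**What to change.** In section 3.5:

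- Keep the exclusion-criterion bullet for on-study events such as pregnancy, anticoagulants or immunosuppression, but exempt systemic antimicrobials given for a study-wound infection. Limiting the bullet to conditions present at enrolment would be wrong, because it would remove the explicit stop for those events.
- Correct *least* to *test* if that is what is meant.
- State that stopping collagen for intolerance or safety does not by itself end participation, and that observation off treatment is not a modified regimen.
- Continue the scheduled non-invasive visits (photographs, measurements, scales, adverse events) if the subject agrees. The investigator may withhold the week-4 re-biopsy or end participation for safety. If collagen has been stopped and the re-biopsy still goes ahead, the new wounds receive standard care and are not counted as treated wounds.

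In section 4.3: keep every wounded subject in the descriptive denominators, show wounds not assessed as such, and list infected or discontinued wounds by treatment.

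The cost is a few sentences and no new visits. For a subject who would otherwise have left between visits 1 and 2, at the rates in section 5.2, travel is at most 5 × $15 = $75. The re-biopsy, if done, is 2 × $125 = $250. The total is $325, which matches the planned $590 less the visit 1 payment: $590 − (2 × $125 + $15) = $325. It is therefore already within the planned payments.

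There is a downside. Healing after a complication also reflects the complication and its treatment, so these results need to be identifiable in the listing. Histology is still missing where the re-biopsy is withheld.

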### **3.6 Strength and Limitations of Proposed Research**

Strengths of the study include its relatively simple design and the potential for its completion within a short period of time due to the small number of participants (eight).

Limitations of this study include the inability to conduct robust statistical analysis due to its small sample size. However, the results of this project may lead to the development of larger studies that will have the statistical power to detect improvements.

## **4. DATA VARIABLES, COLLECTION, AND EVALUATION**

### **4.1 Data Variables**

The following data will be evaluated in patients fulfilling inclusion and exclusion criteria and who agree to participate in the study.

1. ***Sociodemographic Variables:*** Age, gender, and race.
2. ***Clinical History:***
  - a. **Past medical history:** All current and past medical conditions will be documented, allowing us to screen for the presence of any condition that, in the opinion of any of the investigators, would make the patient unsuitable for study inclusion. Allergies to medications will also be noted.
  - b. **Current medications:** All medications will be recorded.
  - c. **Social History:** We will screen for the presence of tobacco product use in addition to any drug or alcohol abuse within the past 6 months as determined by the medical record or patient interview.

### **4.2 Wound specific variables**

**Characterization of wound healing:** Photographs of the wounds will be taken on week 0, 1, 2, and 4, at which time the areas will be re-sampled for histologic analysis, and then photographed again at the 4 week time point, followed by week 6 and then 12. Photographs will be used to follow gross visual wound healing as assessed by the area of the wound uncovered by the migrating epithelia as measured digitally using ImageJ software. Digital measurements will be performed by 2 different members of the research team.

**Morphometric analysis of wound sections:** Wound re-epithelialization will be measured in Hematoxylin and Eosin stained sections from the center of the wound. Dermatopathology procedures will be carried out by HistoWiz, Inc., Brooklyn, NY. The distance between the wound edges, defined by the distance between the first hair follicle encountered at each end of the wound, and the distance that the epithelium had traversed into the wound, will be analyzed using

ImageJ. The percentage of re-epithelialization [(distance traversed by epithelium)/(distance between wound edges) x 100] will be calculated and averaged for 2 sections per wound. The quality of the epidermis and dermis will also be evaluated as a measure of wound maturation at the 4 week time point.

**Collagen deposition:** Dermatopathology procedures will be carried out by HistoWiz, Inc., Brooklyn, NY. Staining will be performed using Masson's trichrome stain and the percentage of blue collagen-stained area relative to the total area of the wound bed after taking digital images. This will be quantified by counting the number of pixels staining above a threshold intensity and normalizing to the total number of pixels.

**Angiogenesis:** Dermatopathology procedures will be carried out by HistoWiz, Inc., Brooklyn, NY. Wound sections will be stained using CD31 antibody (also called platelet-derived endothelial cell adhesion molecule-1). Digital images at 40x magnification covering the majority of the wound bed will be taken. The percent area stained in each image will be quantified by counting the number of pixels staining above a threshold intensity and normalizing to the total number of pixels. Threshold intensity will be set such that only clearly stained pixels are counted. Staining identified as artifact, large vessels, and areas deemed to be outside the wound bed will be excluded.

**Patient Overall Assessment Scale.** Patients will assess the overall improvement of their wounds using a 4-point scale, where 1 = excellent improvement, 2 = good / moderate improvement, 3 = no change, 4 = worsening. This assessment will be performed prior to every follow up visit after wounding at week 0, and upon study completion for each wound. Improvement will be indicated by a decrease by  $\geq 1$  point compared to the previous assessment. Worsening will be indicated by an increase in this scale by  $\geq 1$  point compared to the previous assessment. Patients will also be asked preference between the NuvagenTM (collagen powder) and primary closure.

**Pruritus Numerical Rating (NRS) Scale.** Patients will also score pruritus on the validated NRS scale, which ranges from 1-10. This assessment will be performed prior to every follow up visit after wounding at week 0, and upon study completion for each wound. Improvement will be indicated by a decrease by  $\geq 2$  points compared to the previous assessment. Worsening will be indicated by an increase in this scale by  $\geq 2$  points compared to the previous assessment.

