## **2. BACKGROUND, SIGNIFICANCE, AND RATIONALE**

Wound healing is complex process which requires the restoration of hemostasis, inflammation, proliferation, and remodeling, all of which work in concert to repair the damaged skin barrier in acute wounds. Recent advances in wound therapy have resulted in the development of advanced wound care therapies, such as collagen-based dressings, for use as adjunctive therapies to combat the molecular defects present in wounds.

Collagen is a naturally occurring protein that comprises three-quarters of the weight of human skin. Fibroblasts synthesize collagen molecules, which are composed of three polypeptide chains that together form a triple-helical structure, allowing covalent cross-linking and formation of larger fibrils and fibers. Collagen's unique structure makes it an essential component of the extracellular matrix (ECM), providing remarkable tensile strength and structural support to skin and other connective tissues. During normal wound healing, collagen acts as a scaffold for cellular ingrowth and organized collagen deposition. In addition, proteases that degrade native collagen release polypeptide fragments that act as chemotactic molecules to recruit inflammatory mediators, promote keratinocyte migration, and stimulate the proliferation of fibroblasts and subsequent collagen deposition.

Powdered or fractionated collagen products are developed through a proprietary process that involves the breakdown of natural collagen into smaller components. These collagen particles exhibit minimal cross-linking and are hypothesized to quickly replace degraded collagen fragments by bypassing enzymatic breakdown within the wound environment. Furthermore,

powdered collagen can act as a signaling molecule directly upon application, recruiting inflammatory cells and fibroblasts and supporting keratinocyte migration and ECM production.

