One week after visit 2, the patient will return for visit 3. Sutures will be removed, and the wound treated with collagen will be evaluated for further collagen treatment. The principal investigator will determine if another 2 weeks of Nuvagen™ (collagen powder) treatment will be warranted. If further collagen treatment is advised, the patient will be provided with another 2-week supply of Nuvagen™ (collagen powder) and dressings. Patients will perform the Patient Overall Assessment Score, wounds will be measured, photographs will be taken, and inquiry will be made about any possible adverse events. The wound treated with collagen will be treated and dressed in the office.

Two weeks after visit 3, the patient will return for visit 4. Both wound sites will be photographed and then biopsied again following the procedure from visit 1. Each wound will be treated identically (either with primary closure or with collagen powder) as it was in visit one. Patients will be provided with adequate supplies for at-home collagen treatment for 2 weeks. Patients will perform the Patient Overall Assessment Score, wounds will be measured, photographs will be taken, and inquiry will be made about any possible adverse events.

Two weeks after visit 4, the patient will return for visit 5. Sutures will be removed, and the wound treated with Nuvagen™ (collagen powder) will be evaluated for further collagen treatment. The principal investigator will determine if another 2 weeks of Nuvagen™ (collagen powder) treatment will be warranted. If further collagen treatment is advised, the patient will be provided with another 2-week supply of Nuvagen™ (collagen powder) and dressings. Patients will perform the Patient Overall Assessment Score, wounds will be measured, photographs will be taken, and inquiry will be made about any possible adverse events. The wound treated with collagen will be treated and dressed in the office.

Six weeks after visit 5, the patient will return for visit 6. Patients will perform the Patient Overall Assessment Score, wounds will be measured, photographs will be taken, and inquiry will be made about any possible adverse events.

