### **5.2 Risks and Benefits**

Risks from punch biopsies include the possibility of pain, bleeding, itching, or infection at the biopsy site. Further, there is the possibility of persistent bruising, swelling, or scarring. Pain at the biopsy site will be minimized by use of a local anesthetizing agent. Excessive bleeding will be prevented by excluding patients with known coagulation disorders, patients taking aspirin, or patients taking anticoagulants (including heparin, low molecular weight heparin, warfarin, fondaparinux, or rivaroxaban). Further, bleeding will be minimized by applying adequate pressure using gauze on the biopsy sites. Previous work has shown that wound infections can occur in about 1 in every 6 outpatient skin biopsies. This study failed to subcategorize infection rate for each biopsy type, however, and included patients with medical co-morbidities which contribute to poor wound healing and development of infections. Risk of infection in our study will be minimized by excluding smokers, patients with diabetes mellitus, and patients with other medical or skin conditions that impair wound healing. Collagen is also a poor culture medium and can be left in wounds without risk of enhancing bacterial growth.

Patients may have an allergy or allergic reaction to the numbing agent used, but every attempt to prevent this will be made by asking the patient about his or her allergy history. Furthermore, there is a potential risk of allergy to the interventional type I Nuvagen™ (collagen powder). Although studies have shown that it is possible to develop monoclonal antibodies to mammalian collagen, type I collagen has shown to be very poorly immunogenic. Nonetheless, there have been sparse reports of allergy to topical bovine-derived collagen. Minor amounts of non-collagen proteins in collagen products have also been implicated in immunogenicity of collagen

products. Risk of allergy to the investigational agent used will be minimized further by excluding patients with history of known allergy or sensitivity to any component of the test medication (including bovine and/or collagen products).

There is a potential risk of loss of privacy. All possible precautions will be taken to respect privacy and the confidentiality of patient information, and a secured database with coded identifiers will be used to keep privacy breach risk minimal.

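### The collagen deposition measure has no rule to separate applied collagen powder from new collagen, so any residual product would raise the reading in the powder-treated wound alone

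*Combined protocol and SAP*

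**What the plan says.** Section 4.2 (Wound specific variables), under Collagen deposition, defines the measure on Masson's trichrome as the "percentage of blue collagen-stained area relative to the total area of the wound bed". It then says this is obtained by "counting the number of pixels staining above a threshold intensity and normalizing to the total number of pixels". The paragraph does not delineate the wound bed, lists no exclusions and does not mention applied product.

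The Angiogenesis paragraph that follows uses the same pixel-counting wording for CD31 but adds: "Staining identified as artifact, large vessels, and areas deemed to be outside the wound bed will be excluded". The only wound-edge definition in the section belongs to the H&E re-epithelialization measure, where the span between edges is "defined by the distance between the first hair follicle encountered at each end of the wound".

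Section 5.2 describes the product as type I collagen. Under section 3.4, one wound of each pair receives 1 g on the day of wounding and then daily for 2 weeks, while the contralateral wound is sutured. At visit 3 (week 2) the investigator decides whether to continue: "If further collagen treatment is advised, the patient will be provided with another 2-week supply". Visit 4, two weeks later, is the repeat biopsy for histology.

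Section 1 makes healing judged by week 4 histology the second primary objective. Section 4.3 plans descriptive statistics only, in 8 patients.

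**The concern.** The variable is meant to show collagen laid down by the healing wound. What it counts is stained collagen, whatever its origin, and collagen is also the treatment given to one of the two wounds being compared. The protocol's own rationale puts product in the wound: section 2 says the particles "are hypothesized to quickly replace degraded collagen fragments". In a participant whose treatment is extended, application can continue up to the biopsy. A higher reading in the treated wound could then be a treatment effect, treatment residue, or both, and the stated rule cannot separate them.

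At stake is the interpretation of one histology marker under the second primary objective. No test or decision threshold depends on it. However, section 2 says the histologic markers will be used to judge wound-bed maturity, and that positive findings would suggest powder could replace sutures. With 8 pairs and no inference, readers will take the percentages at face value. A larger later study using the same rule would inherit the same systematic error.

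A second, smaller gap is the scored region. If the bed is not traced, native dermis, which is itself collagen, can be scored along with scar.

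**Working it through.** The plan gives no staining fraction or expected difference, so there is no figure of its own to reproduce. The check compares the relevant texts and then applies mixing arithmetic to assumed values.

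**Text comparison**

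| Item | Trichrome | CD31 |
|---|---|---|
| Nominal region | Wound bed, named as denominator | Wound bed, through the exclusion |
| Count | Pixels above threshold over total pixels | Same wording |
| Artifact excluded | Not stated | Yes |
| Outside the bed excluded | Not stated separately | Yes |
| Applied product addressed | No | No (stain is not for collagen) |

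**Exposure (section 3.4).** The collagen wound receives about 14 × 1 g = 14 g over 2 weeks, or about 28 g if extended to week 4. The sutured wound receives none. Without extension, about 2 weeks pass between the last application and the biopsy.

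**(a) Residual product.** Let t be the true stained share of the bed and q the share covered by residual product, all of it staining above threshold. Both are assumptions.

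Reading = q + (1 − q)t, so the added amount = q(1 − t).

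| q | t = 40% | t = 50% | t = 60% |
|---|---|---|---|
| 2% | 1.2 | 1.0 | 0.8 |
| 5% | 3.0 | 2.5 | 2.0 |
| 10% | 6.0 | 5.0 | 4.0 |
| 20% | 12.0 | 10.0 | 8.0 |

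Entries are percentage points added to the collagen wound only. They apply per affected wound. If product remained in k of the 8 collagen wounds, the mean paired difference would shift by k/8 of the entry. For example, k = 4 with q = 10% and t = 50% gives 4/8 × 5.0 = 2.5 points. If nothing remains, the shift is zero.

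**(b) Native dermis in the scored region.** Suppose the whole 4 mm section were scored. Let w be scar width in mm, s the stained share of scar and d that of native dermis, all assumed.

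Reading = (w/4)s + (1 − w/4)d, so the excess over s = (1 − w/4)(d − s).

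With s = 50%:

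| w | d = 50% | d = 60% | d = 70% | d = 80% |
|---|---|---|---|---|
| 1 mm | 50.0 | 57.5 | 65.0 | 72.5 |
| 3 mm | 50.0 | 52.5 | 55.0 | 57.5 |
| Gap | 0 | 5.0 | 10.0 | 15.0 |

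The gap is (2/4)(d − s). It depends on the assumed staining difference as much as on scar width, and it vanishes when scar and dermis stain alike. Restricting scoring to a traced bed removes (b) but leaves (a) unchanged.

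**The case against.** The strongest reply is that persistence is not shown. Section 2 calls collagen biodegradable and describes the particles as minimally cross-linked. Section 3.4 has the wound irrigated before each home application. Planned treatment lasts 2 weeks, and the documents do not say how many participants would be extended. Nothing states that product is present at week 4 or that it would stain above threshold. All of this stands, and it makes the bias possible rather than demonstrated. It does not supply the missing rule: the plan neither identifies product nor shows that it has gone.

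A reader might infer persistence from the statement in section 2 that collagen can be left in wounds. That statement concerns bacterial growth and says nothing about histology at week 4.

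A reader might also infer that the plan scores all tissue in the section, because the pixel sentence ends with "normalizing to the total number of pixels". The documents do not support that. The preceding sentence names the wound bed as the denominator, and the CD31 paragraph uses the same phrase alongside a wound-bed limit. What remains is an undelineated bed and exclusions that are not repeated. Nor would intact dermis affect only the sutured wound, since it could enter a contracted collagen wound too.

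Finally, trichrome is one of several descriptive markers, and H&E re-epithelialization bears more directly on complete healing. That limits the consequence but does not remove it.

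**Conclusion.** The concern holds for applied product. As written, the rule can count the treatment as the outcome in one wound of each pair, and nothing in the documents separates the two. The size is unknown. Under the stated assumptions (50% true staining, product covering 2% to 20% of the bed and staining above threshold), it is 1 to 10 points per affected wound, and zero if no product remains.

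The region gap is secondary. Its effect would probably be larger in the sutured wound, where apposed edges may leave a narrower scar. It depends on assumed scar width and staining and is zero if scar and native dermis stain alike. It would be tempting to claim a 15-point gap from wound geometry alone, but that figure also needs an assumed 30-point difference in staining and scoring of the whole section, which the named denominator argues against.

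The two errors would tend to raise different wounds, so the net direction of the paired difference cannot be stated. No planned test is affected. What is affected is whether the reading can be interpreted as new collagen. The clarification should be made before slides are scored.

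**What to change.** In section 4.2 (Wound specific variables), under Collagen deposition, specify that:

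- the wound bed is traced on each trichrome image using the matching H&E section, by a reader masked to arm as far as possible;
- pixels inside the traced bed are the only denominator;
- the CD31 exclusions for artifact and tissue outside the bed apply to trichrome as well;
- one intensity threshold is used for both arms, set without knowledge of arm;
- the percentage is reported with and without excluding identifiable acellular foreign collagen, as a sensitivity reading;
- if product cannot be told apart reliably, the variable is labelled collagen-stained area and no conclusion is drawn about new collagen deposition.

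The cost is a short paragraph and annotation of slides already planned. No visit, sample or treatment changes. The downside is reader judgement: the foreign-material exclusion can remove pixels only from the collagen wound, and recognising such material may reveal the arm. That is why both readings are reported and neither replaces the other.
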